There are no additional risks anticipated, specific to participating in this study. The study is not examining any experimental procedures and participation in the study is not predicted to affect the medical treatment received by enrolled subjects. The INFINITY® Total Ankle does not pose additional risks compared to other standard total ankle systems when used for the same clinical application. The risks of ankle replacement include intra-operative complications such as peri-prosthetic fracture, neurovascular damage and tendon injury. Early post-operative problems include infection, wound healing problems, deep vein thrombosis, and peri-prosthetic fracture. Late complications include infection, peri-prosthetic fracture, loosening, implant failure, ongoing pain. These risks are comparable to those in alternative implants and alternative surgical procedures.

STUDY DESIGN

Study Design

The selected design is a multi-center, non-randomized, prospective study of 500 subjects in the UK with ten investigational sites and a potential for more as needed to meet the enrollment requirements. The study subjects included are those with ankle joints damaged by severe rheumatoid arthritis, post-traumatic disease, and degenerative arthritis and implanted with the INFINITY® Total Ankle System.

Primary and Secondary Endpoints

The primary endpoint is a survivorship rate at 10 years as defined with a Kaplan Meier survivorship analysis. Secondary endpoints identify, assess and compare functional improvements or deviations collected through investigator observation and patient self-reporting, and include:

- Identification and assessment of the implant through radiographic assessment for component loosening and/or subsidence, any osteolysis and/or cyst formation early and throughout the lifetime of the implant.

- Comparison of improvements in self-reported pain and social interaction for quality of life measures from pre-op through 10 years post operatively; assessed by EQ5D5L.
- Comparison of pain and functional improvement from pre-op through 10 years in the AOS which is a visual analogue scale specifically designed as a modification of the Foot function Index.
- Comparison of the improvements in self-reported function scores from pre-op through 10 years post-operatively, assessed by MOXFQ walking/standing scores.
- Identification and reporting on the safety of the implant in terms of complications and adverse events.

[figure not shown]

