relevant to the safety and survivorship of the implant but, also to provide assurances that for the introduction of new implants, a data collection plan is in place for ongoing evaluations and reporting.

The information gained from this data collection will be analyzed at times based on potential publication periods around 3, 5, and 7 years with a final analysis after all subjects have completed all follow-up requirements at the 10 year final visit. In addition, at time points determined by the investigators and/or Wright Medical will be evaluated as needed or required for additional analysis of data for reporting and/or publication purposes will be done throughout the study.

Demographics

Descriptive statistics will be applied for the demographic data of all subjects. Pre to post-operative comparisons will be made for all outcome measures at the specific data collection time points. Summary statistics for continuous variables may include subject count, mean, standard deviation, minimum and maximum values.

ADVERSE EVENTS

Suspected Unexpected Serious Adverse Reactions (SUSARS), Serious Adverse Events (SAE's) & ADVERSE EVENTS (AE's)

Procedural and device related events will be described and collected on the AE form. It is the responsibility of the operating surgeon/s to be aware and note the adverse effects from the package insert/instructions for use by the manufacturer/sponsor. (See appendix A) The number of subjects experiencing each adverse event percentage or proportion of the total number of subjects experiencing each adverse event will also be reported. All adverse events shall be reported in an interim and/or final report of the clinical investigation. All device deficiencies related to the identity, quality, durability, reliability, safety or performance of the investigational medical device shall be documented throughout the clinical investigation and appropriately managed by the sponsor.

Potential intraoperative and early postoperative complications, related to all total ankle replacements may include:

- pain;
- sudden drop in blood pressure intra-operatively due to the use of bone cement;
- damage to blood vessels;
- temporary or permanent nerve damage resulting in pain or numbness of the affected limb;
- cardiovascular disorders including venous thrombosis, pulmonary embolism, or myocardial infarction.
- hematoma;
- delayed wound healing; and
- deep wound infection (early or late) which may necessitate removal of the prosthesis.

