- rarely an arthrodesis of the involved joint or amputation of the limb may be required.

Potential, late postoperative complications can include:

- pain;

- bone fracture by trauma or excessive loading, particularly in the presence of poor bone stock;
- peri-articular calcification or ossification, with or without impediment to joint mobility; and
- inadequate range of motion due to improper selection or positioning of components or peri-articular calcification.

Adverse Event Data Collection and Reporting

The following definitions from ISO 14155:2011(E) *Clinical Investigations of Medical Devices for Human Subjects – Good clinical practice*.

Adverse Event (AE)

Any untoward medical occurrence, unintended disease or injury, or untoward clinical signs (including abnormal laboratory findings) in subjects, users, or other persons, whether or not related to the investigational medical device.

Serious Adverse Event (SAE)

Serious adverse events are any adverse events that:

1. Led to death;
2. Led to serious deterioration in the health of the subject, that either resulted in
 - a. A life-threatening illness or injury, or
 - b. A permanent impairment of a body structure or a body function, or
 - c. In-patient or prolonged hospitalization, or
 - d. Medical or surgical intervention to prevent life-threatening illness or injury or permanent impairment to a body structure or a body function

Adverse Event Status Updates (AE)

The Investigator will follow up subjects who experience an AE until it is either resolved, determined to be chronic, stable, or, until the subject's participation in the study ends.

Prior to completion of the study, the Investigator will complete the Adverse Event Status Update Case Report Form to document any AE's previously reported as ongoing.

Recording and Reporting Adverse Events – Investigator Responsibilities

The Investigator will:

- Record protocol required AE's together with an assessment as recorded in the Adverse Event Case Report Forms;
- Supply Wright Medical, upon their request, with any additional information related to the safety reporting of a particular AE

Recording and Reporting Adverse Events – Wright Medical Responsibilities

Wright Medical is responsible for the classification of AEs and ongoing safety evaluation of the study and will:

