- review the Investigator's assessment of all AEs; determine and document, in writing, the seriousness of the adverse event and relationship of the adverse event to the implanted components.

In case of disagreement between Wright Medical and the Investigator, Wright Medical shall:

- communicate both opinions to concerned parties; and
- as required, ensure that the IRB/EC/REC and regulatory authorities are informed or significant new information involving the product during the study.

Recording and Reporting Serious Adverse Events (SAE's) – (Immediately Reportable) Investigator Responsibilities

- The investigator must report the following events to the Sponsor within 24 hours after learning of the event, regardless of relationship to study, using the appropriate SAE reporting form and guidelines;
- The investigator must report new significant follow-up information for these events to the Sponsor within 24 hours after becoming aware of the information. New significant information includes the following:
 - New signs or symptoms or a change in the diagnosis.
 - Significant new diagnostic test results.
 - Change in causality based on new information.
 - Change in the event/s outcome, including recovery.
 - Additional narrative information on the clinical course of the event.

Recording and Reporting Serious Adverse Events (SAE's) – Wright Medical Sponsor Responsibilities

- SAEs must be summarized on the annual report to the Research Ethics committee

Recording and Reporting Suspected Unexpected Serious Adverse Reactions (SUSAR) – Wright Medical Sponsor Responsibilities

Definition - An adverse reaction that is both unexpected (not consistent with the applicable product information) and also meets the definition of a Serious Adverse Event/Reaction

- SUSARs must be reported to the Research Ethics committee in accordance with GCP guidelines i.e. 7 or 15 days

DATA MANAGEMENT

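### When investigator and sponsor disagree on an adverse event, nothing stops the manufacturer-sponsor's lower seriousness or device-relatedness classification from being the one used

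*Protocol*

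**What the plan says.** Under the Protocol heading on investigator responsibilities for recording adverse events, the investigator records events "together with an assessment as recorded in the Adverse Event Case Report Forms". Under the matching heading on the sponsor's responsibilities, "Wright Medical is responsible for the classification of AEs and ongoing safety evaluation of the study". The sponsor is to review the investigator's assessment of every event and then "determine and document, in writing, the seriousness of the adverse event and relationship of the adverse event to the implanted components". If the two disagree, it must "communicate both opinions to concerned parties" and, as required, see that the ethics committee and regulators are informed of significant new information.

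Investigators report serious events to the sponsor within 24 hours, "regardless of relationship to study". The sponsor then owes the ethics committee two outputs: an annual summary of serious adverse events, and SUSAR reports on a 7- or 15-day clock.

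Implant safety is a secondary endpoint: "Identification and reporting on the safety of the implant in terms of complications and adverse events". The opening paragraph of the Adverse Events section says "All adverse events shall be reported in an interim and/or final report of the clinical investigation", and that the "proportion of the total number of subjects experiencing each adverse event will also be reported".

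**The concern.** The party that makes and sells the implant holds the classification role, and it makes its determination after seeing the investigator's. The protocol names no independent adjudicator or safety committee. The disagreement clause governs who is told, not which classification is then counted. An event that the investigator calls serious or device-related could therefore appear in the study's outputs under the sponsor's lower classification without any departure from the protocol.

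This matters because the study follows one implant group with no comparator. A shift in a serious or device-related rate is not offset by a similar shift in another arm; it passes straight into the reported figure. The Study Rationale says that results go to regulatory authorities and notified bodies, and the Sample Size section foresees analyses around years 3, 5 and 7 as well as at the end. The two ethics committee outputs also turn on how an event is classified.

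**Working it through.** The documents give no figure to reproduce. They state no adverse event rate and no disagreement rate, and the sample size of 500 is stated not to have been calculated. The check is therefore to take each output and ask whether it depends on the sponsor's determination.

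1. **Number or proportion of subjects with each adverse event** (Adverse Events, opening paragraph). All events are reported whatever their class. Moving an event from serious to non-serious, or from related to unrelated, does not remove it. *Not affected.* The same paragraph says that procedural and device-related events are collected on the form. That filter acts when the site completes the form, before the sponsor's review.

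2. **Device failure** (section of that name). It is defined by removal of a tibial or talar metal component, which is a surgical fact. *Not affected.*

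3. **Any breakdown by seriousness or by relationship to the implant.** The protocol has both attributes determined by the sponsor and does not say whose classification is tabulated if they differ. *Exposed.*

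4. **Annual summary of serious adverse events to the ethics committee.** Membership depends on seriousness. The text does not say whether an event that only the investigator calls serious is included. *Exposed.*

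5. **SUSAR status.** The definition needs an adverse reaction that is unexpected and meets the serious definition, so it depends on both seriousness and relationship. *Exposed.*

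**Can items 3 to 5 be sized?** Let p be the proportion of subjects with an event that the investigator calls device-related, and d the share of those subjects whose events are all moved down, with none moved up. The reported proportion is p × (1 − d), so the relative understatement is [p − p(1 − d)] / p = d. As an assumed case, take p = 100/500 = 20%. With d = 10%, the report shows 90/500 = 18%; with d = 20%, it shows 80/500 = 16%. The relative understatement of 10–20% simply returns the assumed d. Neither p nor d is in the documents, so this shows the mechanism and is no estimate of its size.

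**Does the disagreement clause close the gap?** It keeps both opinions in existence and communicates them to parties it does not define. It sets no rule for counting, and informing the committee and regulators is qualified by what is required. So it does not.

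**The case against.** A reader might infer that the sponsor's classification is final and overrides the investigator's. The protocol does not say that. The investigator assesses first, the sponsor documents its own view, and both are communicated if they differ. Nor does the text say that the sponsor's view is the one tabulated. What stands is that it leaves this open while giving the sponsor the classification role.

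A reader might also infer that the whole safety endpoint rests on the sponsor's call. It does not: the stated summary covers every adverse event regardless of class, and the protocol names no serious-event or device-related rate as an endpoint. This limits the point to items 3 to 5 above.

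It can be argued that the choice of assessor for a table belongs in a statistical analysis plan, which is not shown. That is fair for tables, and the absence of a tabulation rule is not in itself an error. But the protocol itself assigns the classification role, and the annual summary and SUSAR reporting are not matters that an analysis plan normally governs.

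Finally, several seriousness criteria are largely factual, such as death or hospitalisation, and serious events reach the sponsor within 24 hours whatever their cause. This leaves less room to lower seriousness than to lower relatedness. It does not remove the exposure, and it offers nothing on relatedness, which is a judgement.

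**Conclusion.** The point holds in a limited form. The protocol gives the manufacturer-sponsor the classification of adverse events, has it determine seriousness and device-relatedness after the investigator, and contains nothing to prevent its lower classification from being the one used. Serious and device-related breakdowns, the annual summary of serious adverse events and SUSAR status could be understated. Overall adverse event counts and device failure are not affected.

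The documents do not allow the amount to be sized. Downward reclassification is a risk that the text permits; nothing shows that it happens. The conclusion assumes that investigator and sponsor sometimes disagree, and that no other document already fixes whose classification is used. It is a cheap improvement to the credibility of the safety results and does not threaten the study's primary result.

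**What to change.** Add to the Protocol section on the sponsor's responsibilities for adverse events, next to the disagreement clause: for tabulation, for the annual summary of serious adverse events and for SUSAR reporting, an event counts as serious, or as device-related, if either the investigator or the sponsor so classifies it. Interim and final reports list discordant events with both opinions. The sponsor can then still raise a classification, but lowering one no longer changes what is counted. The test of unexpectedness in the SUSAR definition stays as it is.

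The change needs no new staff or procedure, because the investigator's assessment is on the case report form and the sponsor's is documented in writing. This assumes that the form, which is not shown, records the investigator's view of both seriousness and relationship; that should be confirmed. Stating which assessor is analysed, tabulating both, or independent adjudication would also settle which classification is reported. The either-party rule is preferred because it uses what is already recorded and cannot understate relative to the investigator. The price is that serious and device-related figures may be slightly less favourable.
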